To explore the preliminary impact of NDURE compared with UC on completion of adjuvant therapy	PORT duration, defined as the number of days from the initiation of PORT to the completion of PORT among patients who complete the intended course of adjuvant therapy.
	Completion of intended course of PORT, defined as receipt of the planned PORT dose (total Gy)
To explore the preliminary clinical impact of NDURE compared with UC on decreasing barriers to timely PORT.	Percent of total barriers on PBQ that are resolved
	Number of unresolved barriers on PBQ
	Reason for PORT delay
To explore the preliminary behavioral mechanism of action of NDURE.	CTM-15 scale score
	Change from baseline in 
 ISEL-12 scale score Perceived Susceptibility scale score IPQ-R Consequences scale score CASE-Cancer scale score

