8.3 NON-BASELINE CLINICAL CHARACTERISTICS

Additional oncologic details related to the course of clinical care will be collected from the EMR. For patients receiving portions of their care outside of MUSC, appropriate clinical records will need to be collected.

Additional non-baseline oncologic characteristics include date of definitive surgery, type of ablative surgery, type of surgical reconstruction, AJCC 8th edition pathologic TNM Class, AJCC 8th edition overall pathologic stage grouping, adverse pathologic features (margin status, perineural invasion, extranodal extension), facility delivering the adjuvant therapy, planned radiation dose (Gy), delivered radiation dose (Gy), presence (and type) of chemotherapy, date of completion of radiation therapy.

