Time from Surgery to Postoperative Appointment with Radiation Oncology is defined as the time, in days, from the date of definitive surgery to the date that the patient attends a postoperative appointment with radiation oncology. For patients who have seen a radiation oncologist prior to surgery, this measure refers to the scheduling of the post-operative follow-up appointment with the radiation oncologist. In situations in which a patient is re-referred postoperatively (i.e., a patient is referred to a radiation oncologist at one facility and then decides to get treatment at a different facility), the measure is evaluated using the time to the second referral. In situations in which an appointment is scheduled but the patient does not attend the appointment, the measure is evaluated using the date for which the appointment was actually attended.

PORT Duration, defined as the number of days from the initiation of PORT to the completion of PORT among patients who complete the intended course of adjuvant therapy.

Completion of intended course of PORT, defined as receipt of the planned PORT dose (total Gy).

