9.4.2 MISSING DATA

- PORT delay status (delay or timely PORT) will be considered 'delayed' for any evaluable patient with missing PORT delay status.
- TTP will be right-censored for evaluable patients who die prior to PORT initiation, are lost to follow-up prior to PORT initiation, or who haven't received PORT by the end of follow-up (18 weeks postoperatively).
- TPT will be right-censored for evaluable patients who die or are lost to follow-up prior to the conclusion of PORT, or who prematurely discontinue their intended course of PORT. TPT will also be right-censored for patients who have not completed PORT by the end of follow-up (18 weeks postoperatively).
- Time from surgery to PORT referral scheduling will be right-censored for evaluable patients who die prior to PORT initiation, are lost to follow-up prior to PORT initiation, or who haven't received PORT by the end of follow-up (18 weeks postoperatively).
- Time from surgery to appointment with radiation oncology will be right-censored for evaluable patients who die prior to PORT initiation, are lost to follow-up prior to PORT initiation, or who haven't received PORT by the end of follow-up (18 weeks postoperatively).

- Analyses of exploratory endpoints will be conducted using complete case analysis.

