9.4.9 EXPLORATORY ANALYSES

For other exploratory endpoints (e.g., health behavior constructs), data will be summarized using frequency and percent for categorical variables and using mean, median, standard deviation, IQR and range for continuous variables. We will construct 90% CIs to provide a measure of uncertainty in estimated proportions and means. Comparisons between trial arms of other exploratory endpoints will be performed using *t*-tests and chi-square tests, or Wilcoxon rank sum and Fisher's exact tests as appropriate. Pre- and post-intervention values of variables measuring the theoretical constructs underlying NDURE (i.e. care coordination, self-efficacy in cancer care, support, and knowledge) will be compared using Wilcoxon sign rank tests. Comparisons between arms of the change in scores will be conducted using Wilcoxon rank sum tests.

For the exploratory endpoints of barrier reduction and unresolved barriers, we will calculate the proportion of unresolved barriers and the frequency of unresolved barriers (respectively) at the end of NDURE, consistent with prior PN studies⁵¹. We will use logistic regression to assess the association between unresolved barriers and the rate of PORT delay (primary endpoint), controlling for randomization stratification variables.

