6.0	10/15/23	
 -Added new secondary (treatment package time) and exploratory (PORT duration, completion of intended PORT, reason for PORT delay) endpoints -Added detail about definitions of secondary and exploratory endpoints -Deleted unnecessary text from overall design -Clarified relationship between eligibility criteria, criteria for participant discontinuation, and evaluable populations for analysis -Clarified prioritization between inflated sample size and sample size for PORT delay analysis set if inflated sample size was not sufficiently conservative -Added section on missing data and corresponding analyses for new secondary and exploratory endpoints 	
 -Address concern that shorter time-to-PORT could lead to unintended breaks during PORT -Address ambiguity in definitions of endpoints -Text was in wrong section of protocol and duplicative with text in proper section of protocol -Address inconsistencies regarding best way to define criteria in question -Address ambiguity about target sample size -Address deficiencies in prior protocol and harmonize statistical analysis section with protocol changes described above
7.0	12/15/31	
 -Harmonized end-of-study definition with secondary endpoint of treatment package time Updated definition of time-to-PORT to ensure that lengthy delays in initiating PORT would be captured within the data 	
 -Failed to harmonize end-of-study definition with endpoint of treatment package time at time of prior amendment adding treatment package time -Failure to consider longer time-to-PORT options in original definition of the endpoint

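### PORT duration in raw calendar days mixes the planned course length with unplanned breaks, and its completer condition is ambiguous; days beyond the planned course would measure breaks better

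*Combined protocol and SAP*

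**What the plan says.** Section 8.4.6 gives the definition: calendar days, counted from the start of PORT, up to "completion of PORT among patients who complete the intended course of adjuvant therapy". Table 2 (Section 3) repeats it as an exploratory endpoint under the objective "To explore the preliminary impact of NDURE compared with UC on completion of adjuvant therapy". The next definition in Section 8.4.6, completion of the PORT course, depends only on whether the planned dose in Gy was received.

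The version 6.0 entry in Section 10.4 gives the reason for the addition: "Address concern that shorter time-to-PORT could lead to unintended breaks during PORT". It covers four endpoints: treatment package time (secondary), and PORT duration, completion of intended PORT and reason for PORT delay (exploratory). The log is used here only for the purpose; the definition at issue is current text.

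PORT duration has no analysis paragraph of its own, so the general exploratory plan applies. Section 9.4.9 states: "Comparisons between trial arms of other exploratory endpoints will be performed using" two-sample tests (t, chi-square, rank-sum or Fisher), with no covariates. Section 9.4.2 adds: "Analyses of exploratory endpoints will be conducted using complete case analysis".

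Section 8.3 lists the course data collected: "planned radiation dose (Gy), delivered radiation dose (Gy), presence (and type) of chemotherapy, date of completion of radiation therapy". It lists no planned number of treatments, planned end date or count of missed treatment days.

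**The concern.** The question is whether starting PORT sooner leads to interruptions. Total days answer a different one, because they are the sum of the planned course and any unplanned prolongation. A longer course given without interruption and a shorter course with a break can score the same. The planned dose is recorded for each patient but does not enter this endpoint or its comparison.

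The population condition is a second difficulty. Elsewhere the protocol plans PORT with or without chemotherapy (Section 5.1, criterion 7), and Table 1 lists the type of adjuvant therapy separately from the PORT completion date. Taken literally, completing adjuvant therapy therefore includes completing chemotherapy. A patient who received every planned Gy but stopped chemotherapy would be left out, and such patients may have had more toxicity.

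At stake is how informative this pilot can be about a possible harm that its own authors named, before a definitive trial is designed.

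**Working it through.** **Plan's own figure.** The documents give no SD, effect size or power for PORT duration, so there is nothing to reproduce.

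**Do the companion endpoints fill the gap?**
- Completion of planned dose: a patient who has a long break and then finishes counts as complete.
- Treatment package time: it runs from surgery, so it contains the interval that NDURE aims to shorten. Starting five days earlier and then having a five-day break cancel out.
- Reason for PORT delay: it concerns the start of PORT, not interruptions during it.

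Only PORT duration could isolate breaks.

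**Precision.** Write D = P + B, where P is prescribed length and B is unplanned prolongation. Let a share m of patients have a course g days longer, and let B have SD u. With P and B independent, the share of Var(D) due to prescription is m(1-m)g² / [m(1-m)g² + u²]. All three inputs are assumed: m = 0.3-0.5, g = 4-7 days, u = 3-6 days.
- Low end: 0.21×16 / (0.21×16 + 36) = 3.36/39.36 = 0.09.
- High end: 0.25×49 / (0.25×49 + 9) = 12.25/21.25 = 0.58.

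**Simulation.** Rank-sum test, 3,000 runs, two-sided 0.10 (matching the 90% intervals of Section 9.4.9; Section 9.4.1 names 0.05, at which power would be lower). There are 65 completers per arm, an assumed figure below the 75 evaluable patients per arm in Section 9.2.2. P is a common base plus 0-2 random days, plus L days in a share q of patients. Breaks last 3-7 days, mean 5, so break rates of 35% against 15% move the mean by 0.20×5 = 1.0 day.

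Same prescription mix in both arms:

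| q | L (days) | Break rates | Rejection, raw days | Rejection, days beyond plan |
|---|---|---|---|---|
| 0.5 | 5 | 15% / 15% | 0.103 | 0.097 |
| 0.2 | 3 | 35% / 15% | 0.61 | 0.84 |
| 0.3 | 5 | 35% / 15% | 0.48 | 0.84 |
| 0.5 | 5 | 35% / 15% | 0.44 | 0.86 |
| 0.5 | 7 | 35% / 15% | 0.31 | 0.86 |

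Error stays at its nominal level, and power falls.

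Mix made to differ by arm (L = 5):

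| Mix | Break rates | Mean difference, raw days | Rejection, raw | Rejection, beyond plan |
|---|---|---|---|---|
| 55/45 | 15% / 15% | 0.5 | 0.22 | 0.10 |
| 60/40 | 15% / 15% | 1.0 | 0.54 | 0.09 |
| 60/40 | 15% / 35% | 0.02 | 0.11 | 0.84 |

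These rows show what an imbalance would do. They do not show that one exists.

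**Chance imbalance.** The SD of the arm difference in mean prescribed length is L√(2q(1-q)/n). For L = 5, q = 0.5, n = 65 it is 5√(0.5/65) = 0.44 day, a 90% range of ±1.645×0.44 = ±0.72 day. Over q = 0.2, L = 3 to q = 0.5, L = 7 the range runs from ±0.35 to ±1.01 days. This is noise already inside the 0.103, but it is sizeable beside a 1.0-day signal.

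**Completer condition, literal reading.** If 40-60% receive chemotherapy and 20-40% of those stop it (both assumed), the share excluded is 0.4×0.2 = 0.08 to 0.6×0.4 = 0.24. If 20% against 10% of the arms stop, and breaks occur in 50-80% of stoppers and 15% of others, the true difference in break rate is 0.10×(0.50-0.15) = 0.035 to 0.10×(0.80-0.15) = 0.065. Among completers it is zero.

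**The case against.** The case against is substantial, and much of it stands.

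- **The endpoint carries little formal weight.** It is exploratory, in a pilot, and one of four endpoints added under the same rationale. A reader might infer that it is the trial's designated test for this harm. The documents do not say so.
- **Variation in course length is inferred.** Planned dose has to be recorded anyway to score the completion endpoint. The only course length mentioned is about six weeks, in the travel-support text of Section 6.1.1.1 and Table 3. No distribution of prescriptions is given.
- **A reader might infer that the arm comparison is biased and that prescription differences will be reported as breaks.** The documents do not support that. Randomization balances prescriptions in expectation and is stratified by predicted facility (Section 6.3). A route to imbalance exists: NDURE helps the patient choose a facility and may provide housing near MUSC, whereas under usual care facility choice is not discussed before surgery (Section 6.1.1.1, Table 3). But nothing links facility to course length.
- **A reader might also infer that patients who stop chemotherapy are certainly excluded.** Usage is mixed. Section 8.2.2 describes the same stratifier as the facility for adjuvant therapy and as the PORT facility, and both endpoints under the Table 2 objective concern PORT. That chemotherapy completion is not collected suggests that PORT completion was meant. This is an ambiguity, not a demonstrated exclusion.
- **Analysing only patients who receive the planned dose still selects after randomization.** It omits those who break off and never finish, so non-completers must be reported alongside.

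None of this removes the mismatch between purpose and measure. Adjusting for planned dose would help in part, but dose alone does not give planned calendar length.

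**Conclusion.** The point holds in a limited form. The one listed endpoint that could isolate treatment breaks is defined so that breaks are added to planned length, and no planned analysis separates them. If prescribed lengths vary, the expected consequence is lost precision: under the scenarios tried, power roughly between a third and three-fifths, where days beyond plan would give about 0.85. Bias is conditional on an arm difference in prescriptions that the documents make plausible but do not establish. A null result on raw days would be weak reassurance, though not worthless.

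The completer wording needs to be settled whichever reading was meant.

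Every magnitude rests on assumed break rates, course-length gaps and chemotherapy figures, and on planned duration being recorded without error. They illustrate sensitivity and are not estimates for this trial. The primary and secondary results are untouched. This is a cheap improvement to an exploratory endpoint.

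**What to change.** In Section 8.4.6 and Table 2:

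1. Record planned PORT duration from the radiation record (planned number of treatments and schedule, or planned end date).
2. Define the compared quantity as actual days from first to last PORT treatment minus planned days, and compare it between arms with the two-sample tests already in Section 9.4.9.
3. Base the population on receipt of the planned PORT dose, replacing 'adjuvant therapy' with 'PORT' so that it matches the neighbouring completion endpoint.
4. Report by arm, next to this result, the patients who start PORT and do not receive the planned dose.
5. Keep raw duration as a descriptive row.

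The cost is one or two eCRF fields and the wording changes. Section 8.4.4 already provides for obtaining outside treatment records at the end of adjuvant therapy, so no visits are added and care does not change.

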8.4.7 HEALTH BEHAVIOR CONSTRUCT ASSESSMENTS

Health behavior construct data will be collected using validated measures of each construct to explore the potential behavioral mechanisms underlying NDURE.

Modified Care Transition Measure-15 (CTM-15): The CTM-15 is a validated, psychometrically sound 15-item, unidimensional measure of care transitions across the healthcare system that is consistent with the concept of patient-centeredness and useful from an organization perspective for the purpose of performance measurement and quality improvement⁵³. The CTM-15 was modified to evaluate care transitions around PORT delay. 3 questions related to medications at time of hospital discharge were removed to create a 12-item measure. Items are rated on a 4-point Likert scale from 'Strongly Disagree' (1) to 'Strongly Agree' (4). Total score, reported out of 100, is calculated as the mean score (the summed score from each question divided by the total number of questions) with a linear transformation to 100; higher scores reflect more care integration and better care transitions.

Interpersonal Support Evaluation List-12 (ISEL-12): The ISEL-12 is a validated, 12-item assessment of interpersonal support across three domains (appraisal, belonging, and tangible)⁵⁴ that has been used to assess support in prior PN studies⁵⁵. Items are rated on a 4-point Likert scale from 'Definitely False' (1) to 'Definitely True' (4). The score is calculated by summing scores across all items (with reverse coding for items 1, 2, 7, 8, 11, 12). Scores range from 12-48 higher scores indicate greater interpersonal support.

Perceived Susceptibility Questionnaire: The Perceived Susceptibility Questionnaire is a validated 3-item perceived susceptibility subscale for mammography screening⁵⁶ that has been modified to assess perceived susceptibility for delays starting PORT after HNSCC surgery. It consists of two subscales. The first subscale consists of two questions, one assessing absolute perceived susceptibility to delays starting PORT and the other assessing relative perceived susceptibility to delays starting PORT. Items are rated on a 5-point Likert scale from 'Strongly Disagree' (1) to 'Strongly Agree' (5). The score of the subscale is calculated by summing scores across all items. Total scores for the subscale range from 2-10. Higher scores indicate greater perceived susceptibility to delays starting PORT. The second subscale is a single item assessing the cognitive evaluation of absolute perceived susceptibility to PORT delay. The item is measured as a continuous measure from 0 (no chance of delay) to 100 (guaranteed delay). Scores on this subscale range from 0-100 with higher scores indicating a greater perceived susceptibility to PORT delays.

Illness Perception Questionnaire-Revised (IPQ-R) Consequences Subscale (HNSCC Modification): The IPQ-R is a validated assessment of a patient's self-representation of the health consequences of their illness that consists of 8 separate subscales⁵⁷. The IPQ-R Consequences Subscale is easily modifiable to assess disease-specific perceived severity⁵⁸. The HNSCC Modification of the IPQ-R Consequences Subscale consists of 6 questions. Items are rated using a 5-point Likert scale from 'Strongly Disagree' (1) to 'Strongly Agree' (5). The score is calculated by summing across all items (with reverse coding for item 3). Scores range from 5 to 30. Higher scores indicate a greater degree of perceived severity of the illness.

Communication & Attitudinal Self-Efficacy Scale (CASE)-Cancer: The CASE-Cancer is a validated, psychometrically sound 12-item scale that addresses three domains of self-efficacy in cancer care (understanding and participating in care, maintaining a positive attitude, and seeking and obtaining information)⁵⁹. The CASE-Cancer scale has been used extensively in PN studies to measure perceived self-efficacy^{10,44,52}. Responses are on a 4-point Likert scale from 'Strongly disagree' (1) to 'Strongly Agree' (4). Scores range from 12-48; higher scores indicate greater levels of self-efficacy in cancer care.

8.5 ADVERSE EVENTS AND SERIOUS ADVERSE EVENTS

8.5.1 DEFINITION OF ADVERSE EVENTS

This trial is considered to carry a low risk to subjects (i.e. has a "no more than minimal risk" designation). As such, this protocol defines an adverse event (AE) as any undesirable sign, symptom, medical, psychological, social, or emotional reaction that is definitely, probably, or possibly related to the study intervention (as described in 8.5.3). Post-surgical treatment toxicity (wound complications, hospital readmissions, etc) is expected for the NDURE and UC care groups and known to be associated with the primary endpoint (PORT delay).⁶⁰ Although it is not hypothesized that the NDURE intervention will decrease the risk of treatment toxicity, it is hypothesized that NDURE will improve patient-provider communication and care coordination about treatment toxicity, thereby decreasing the risk of PORT delay. As a result, data about expected post-surgical treatment toxicity (wound-healing complications, need for additional surgery, unplanned visits to the emergency room, and unplanned hospital readmissions) are assessed in the PBQ-P and PBQ-N (Section 8.4.5) to allow for specific comparison of these types of events between the NDURE and UC arms and their relationship with the primary endpoint (PORT delay).

